4.3.1 Secondary Analysis

The secondary endpoint analyses will consist of the following:

Two tests of the primary endpoint in the mITT population, but expanded to be defined as freedom from AF/AT, with or without AADs, 12 months after one or two procedures. A superiority hypothesis will be tested using a Cox proportional hazards model with randomization group, AF duration, and AF/AT strata as fixed effects, with a one-sided alpha level of 0.025:

Both analyses under will be evaluated according to the following hypotheses:

$$H_0$$
: $S_1(t) = S_2(t)$

$$H_A$$
: $S_1(t) > S_2(t)$,

where $S_1(t)$ and $S_2(t)$ represent the survival functions for the Tailored and Anatomical arms, respectively, at any given time t. If the null hypotheses for each of the tests is rejected, the following superiority statements will be considered on behalf of each endpoint:

- 1. Tailored ablation is superior to anatomical with respect to freedom from AF/AT, with or without AADs, 12 months after one or two procedures.
- 2. Tailored ablation is superior to anatomical with respect to freedom from AF/AT, with or without AADs, 12 months after one procedure.

Similarly to the primary endpoint analyses, Cox Proportional hazards regression models will be fit and assessed for goodness-of-fit. Then to test each null hypothesis, one-sided Log-Rank Tests will be. Just like under the primary analysis, the p-value from the one-sided Log-Rank Test run under each Cox Proportional hazards model will ultimately be what is used to either reject (p < 0.025) or fail to reject ($p \ge 0.025$) the null hypotheses above. Both Cox models will be conducted in the mITT population.

Kaplan-Meier plots will be generated for each endpoint, to visually display the differences among the survival distributions of the Tailored and Anatomical arms, respectively, with each plot accommodated by the p-value generated from their respective one-sided Log-Rank test.

3. The composite adverse event (AE) rate defined as the number of AEs per month occurring in each treatment arm from time of index procedure through to 12-month follow-up, where composite AEs are defined by either death, a cerebrovascular event, or any serious procedure-related adverse event, will be conducted. in the Safety population (see Section 4.5, Safety Endpoints below).

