4.5 SAFETY ENDPOINTS

The safety endpoint is a composite endpoint at 12 months of the following: death, cerebrovascular events, or serious treatment-related adverse event. Because the rates of this endpoint which are observed under each of the study arms may or may not prove to be relatively rare (< 5% within a given arm), two methods of analysis are provided, the one which will ultimately be used to analyze the safety endpoint will depend on its rate of occurrence, as observed across the two study groups. The safety endpoint analysis, regardless of the method employed, will be conducted in the Safety population. The same analysis will also be conducted in the mITT and PP populations, since if rare occurrence of the safety endpoint is observed and the few occurrences observed happen to all occur within the mITT/PP populations, then the smaller subject sample sizes will serve to increase the rates/proportions observed in each study arm.

METHOD 1 (safety endpoint occurrence > 5% in each study arm):

The safety analysis will be to compare the AE composite rate per month (defined as the 4th secondary endpoint in Section 1 Protocol Summary) under the Tailored (treatment) arm against the Anatomical (control) arm AE composite rate per month from the time of index procedure until the 12-month follow-up. A two-sided 95% CI will be generated for the rate ratio (λ_t/λ_c) comparing the AE composite rate for the two study arms.

Let λ_c and λ_t denote the rate of composite adverse events for the Anatomical and the Tailored treatment arms, respectively. Given a non-inferiority margin δ , the null and alternative hypotheses are:

$$H_0: \frac{\lambda_t}{\lambda_c} \ge 1 + \delta$$

$$H_1: \frac{\lambda_t}{\lambda_c} < 1 + \delta$$

 λ_t,λ_c , and $\frac{\lambda_t}{\lambda_c}$ will be estimated with a linear fixed effects model with a log link function and a Poisson distribution for the number of adverse events (referring only to those defined under the composite AE endpoint). The outcome of the model is the number of composite AEs for each subject enrolled and randomized to one of the study arms. The model will

include an indicator variable for Study Arm, an offset for the log of the number of weeks each subject remained enrolled in the study will be added (the date of each subject's index procedure will be regarded as their first day on the study). In the event the model fails to converge, it will be refit with a Negative Binomial distribution.

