 H_0 is rejected if the upper limit of the 95% confidence interval for $\frac{\lambda_t}{\lambda_c}$ is less than $1+\delta$. If H_0 is rejected, non-inferiority is demonstrated. Based upon the number of months and the expected rate of adverse events, the current study design is under-powered to detect a clinically meaningful (less than 5%) non-inferiority margin for the Tailored treatment arm. Because the null hypothesis test must be conducted under a specified non-inferiority margin, the analysis will use $\delta=0.05$.

METHOD 2 (safety endpoint occurrence (≤ 5% in each study arm):

If both model approaches fail to converge, most likely due to the incidence of the composite AE rates being relatively rare (less than or equal to 5%) under both study arms, then the composite AE endpoint will be treated as a frequency instead of a rate, such that P_1 will be used to denote the proportion defined by the number of composite AEs out of total subjects in the Tailored (treatment) arm and P_2 will be used to denote the proportion defined by the number of composite AEs out of total subjects in the Anatomical (control) arm. The difference in proportions ($P_1 - P_2$) will be reported along with a two-sided exact 95% CI using an exact test statistic with continuity correction if not already defaulted (a Fisher's Exact test may be used if CI can be generated from its statistic for the difference of proportions estimate). Given a non-inferiority margin δ , the null and alternative hypotheses are as follow:

$$H_0: p_1 - p_2 \ge \delta$$

 $H_1: p_1 - p_2 < \delta$

If the upper bound of the 90% CI for (P_1-P_2) is less than $\delta=0.025$, the null hypothesis is rejected, and non-inferiority is demonstrated (2.5% has been allocated as a clinically meaningful non-inferiority margin in the absence of literature). In the event that the composite AEs have a zero occurrence in both study arms, a confidence interval for the difference of proportions cannot be computed, in which case 95% exact CIs for P_1 and P_2 will be reported, and non-inferiority will be considered demonstrated.

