4.5.1 Other Adverse Events

All adverse events will be summarized through 12 months. The proportions of subjects with events will be reported. No imputation for missing data is planned.

Tabular summaries by treatment group of all adverse events, adverse device effects, serious adverse events, and serious adverse device effects will be presented.

An adverse event (AE) is defined as any untoward medical occurrence, unintended disease or injury or untoward clinical signs (including an abnormal laboratory finding) in subjects,

users or other persons, whether or not related to the investigational medical device. An Adverse Device Effect (ADE) is defined as an adverse event related to the use of an investigational medical device. A serious adverse event (SAE) is an adverse event that:

- a) led to a death
- b) led to a serious deterioration in the health of the subject, that either resulted in: a life-threatening illness or injury, or a permanent impairment of a body structure or a body function, or in-patient or prolonged hospitalization, or -medical or surgical intervention to prevent life threatening illness or injury or permanent impairment to a body structure or a body function.
- c) led to fetal distress, fetal death or a congenital abnormality or birth defect. A serious adverse device effect (SADE) is an adverse device effect that has resulted in any of the consequences characteristic of a serious adverse event.

The investigator will assess each adverse event for its relationship to the study device, and whether it was anticipated in the protocol. The determination of the relationship between the adverse event and the device is made according to the following definitions:

- Definitely related (causal relationship)
- Probably related
- Possibly related
- Not related
- Unknown.

Acute peri-procedural complications (related to the study procedure and occurring within one week of the ablation procedure), will be specifically analyzed as part of the exploratory endpoints.

5 Assessing the Primary Outcome

Freedom from documented AF between 3 and 12 months following the index ablation procedure will be defined as no documented episodes of AF > 30 seconds with conventional non-invasive monitoring.

The following scenarios result in primary endpoint failure:

- 1) A repeat procedure where AF is confirmed during the procedure (Patient is in spontaneous AF at the beginning of the procedure)

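### Safety Method 2 puts composite events over subjects and then analyses the ratio as a binomial proportion, so one patient with several events can change the non-inferiority decision

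*SAP*

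**What the plan says.** The endpoint, in SAP 4.5: "The safety endpoint is a composite endpoint at 12 months of the following: death, cerebrovascular events, or serious treatment-related adverse event".

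For Method 2, the same section defines P1 as "the proportion defined by the number of composite AEs out of total subjects in the Tailored (treatment) arm" and P2 as "the proportion defined by the number of composite AEs out of total subjects in the Anatomical (control) arm". The difference is to be reported with an exact interval, with Fisher's test as a possible alternative. Non-inferiority is declared if the upper bound of a 90% interval is below 0.025. On that margin the SAP says "2.5% has been allocated as a clinically meaningful non-inferiority margin in the absence of literature".

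Events are also the counting unit elsewhere for this endpoint. SAP 4.3.1 has "The composite adverse event (AE) rate defined as the number of AEs per month occurring in each treatment arm", and Method 1 has "The outcome of the model is the number of composite AEs for each subject enrolled and randomized to one of the study arms".

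The only patient-level wording is in SAP 4.5.1, on other adverse events: "The proportions of subjects with events will be reported". Protocol 4.2 names the composite without a counting rule, and SAP section 3 gives the SAP precedence over the protocol. Neither document says that a patient counts once, that only the first event counts, or that linked events are merged.

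**The concern.** Counting events suits Method 1, which models a count per subject with an offset for time. It does not suit Method 2. An exact interval for a difference in proportions, or Fisher's test, assumes that each subject contributes a single 0 or 1. With events in the numerator, a second or third event in one patient is treated as if another patient had been affected.

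More than one event per patient is plausible. Protocol 14.3 lists cardiac tamponade, stroke/TIA and death as separate anticipated events, and Protocol 5.3.7 allows a redo procedure within the 12 months. Method 2 is written for few events per arm, which is where one or two extra counts matter most. At stake is the formal statement that non-inferiority on safety has been demonstrated.

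**Working it through.** **Inputs.** SAP 4.2.2 plans 374 subjects, 187 per arm, from 292 (146 per arm) and 22% drop-out: 292 / 0.78 = 374.4, which reproduces the plan's figure. The documents give no expected event rate or power for Method 2, and no size for the Safety population. I assume 187 per arm and check 146. The 5% ceiling is 0.05 × 187 = 9.35, so at most 9 per arm (0.05 × 146 = 7.3, so at most 7). The margin is 0.025, and the decision bound is the upper end of a 90% interval (z = 1.645). All event counts below are assumptions.

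**Formulas,** with p1 = x1/n, p2 = x2/n and n subjects per arm:

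- Wald: p1 − p2 + 1.645 × √[p1(1−p1)/n + p2(1−p2)/n]. The continuity-corrected form adds ½(1/n + 1/n) = 1/187 = 0.00535.
- Score (Miettinen-Nurminen): the value of d at which (p1 − p2 − d)/√V(d) = −1.645. V(d) uses the rates fitted under a difference of d, times 2n/(2n − 1).
- Exact: unconditional one-sided p-value at a difference of 0.025, ordered by the score statistic and maximised over control rates from 0 to 12%. Non-inferiority is met if p ≤ 0.05.

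Wald for 2 vs 2: p1 = p2 = 2/187 = 0.0107, so the limit is 0 + 1.645 × √(2 × 0.0107 × 0.9893/187) = 0.0175.

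| Tailored vs Anatomical, 187 per arm | Wald | Wald, corrected | Score | Exact p |
|---|---|---|---|---|
| 2 vs 2 (patients) | 1.75% | 2.28% | 2.24% | 0.037 |
| 4 vs 2 (same patients, one Tailored patient with three events) | 3.20% | 3.74% | 3.74% | 0.184 |
| 3 vs 2 (patients) | 2.49% | 3.02% | 3.01% | 0.091 |
| 3 vs 4 (same patients, one Anatomical patient with three events) | 1.77% | 2.30% | 2.08% | 0.031 |

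**Against Tailored.** 2 vs 2 meets the margin by all four methods, and 4 vs 2 fails by all four.

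**In favour of Tailored.** 3 vs 2 fails by corrected Wald, score and exact, and 3 vs 4 passes by all of them. Plain Wald already passes 3 vs 2, at 2.49%, so this reversal does not appear under that method. The SAP asks for an exact interval, not plain Wald.

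**Other settings.** With 146 per arm, 1 vs 2 passes (score 1.79%, exact p 0.025). One Tailored patient with three events makes it 3 vs 2, which fails (3.83%, p 0.165). With 187 per arm and one-sided 2.5%, the level of the reported 95% interval, 1 vs 2 passes (exact p 0.014) and 3 vs 2 fails (p 0.091).

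**How tight the boundary is.** With 187 per arm, the largest Tailored count that passes the exact test at one-sided 5% is 1, 2, 2, 3, 3, 4, 5, 5 and 6 for Anatomical counts of 1 to 9. Near this boundary, one or two extra events decide the test.

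**Choice of method.** The counting unit can also move an arm across the 5% line. Eight patients with ten events are 8/187 = 4.3% by patient and 10/187 = 5.3% by event.

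**The case against.** The strongest reply is that patients were meant. Method 2 announces a move from a rate to a frequency, and then uses proportions, exact intervals and Fisher's test, all of which presuppose one result per subject. On that view the event wording is a carry-over from Method 1. This may well be the intention, and it is why a change of wording is enough. But the literal definition is given twice, once per arm, and nothing overrides it. If the unit is left open, it could be chosen after the counts are known.

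Second, Method 2 may rarely be reached. Its heading, and the opening of SAP 4.5, tie the choice to an observed rate of about 5%. The body text says that it applies if both count models fail to converge. A Poisson model with only an arm term and an offset has finite estimates whenever each arm has at least one event. If convergence alone governed, the examples above would therefore be handled by Method 1. This stands: the examples rest on the 5% reading.

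Third, a reader might infer that a single procedural stroke is counted two or three times because it meets several components. The documents do not support this. SAP 4.3.1 makes an event qualify by any one criterion, so a stroke that is both cerebrovascular and procedure-related is one event. The definition of a serious event treats death as something the event led to. Protocol 14.3 does require death to be reported as a serious event, so a separate record of the death is possible but not certain. The examples need separately recorded events, and the documents give no likelihood for that.

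Finally, patient-level proportions would be reported under SAP 4.5.1, so a discrepancy could be noticed. That helps the reader of the report, but it does not alter the decision rule.

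**Conclusion.** The definition is wrong as written for the methods applied to it, and it should be corrected before the analysis. When a patient has more than one separately recorded composite event, the Method 2 interval is not valid, and the non-inferiority decision can change in either direction. In the examples the upper limit moves from 2.24% to 3.74%, or from 3.01% to 2.08%, against a margin of 2.5%.

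This rests on an assumed 187 per arm, assumed counts, the 5% reading of when Method 2 applies, and score limits. The exact test used here agrees on all four decisions, though the SAP does not say which exact procedure it intends.

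A reader might infer that the trial's safety conclusion is unreliable in general. That does not follow. A reversal needs the Method 2 branch, a patient with several events and counts near the margin, all together. It concerns a secondary endpoint and leaves the primary endpoint, its significance level and the sample size untouched.

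**What to change.** In SAP 4.5 Method 2, define P1 and P2 as the number of subjects with at least one composite event from the index procedure through 12 months, divided by the number of subjects in that arm of the analysis population. That is the Safety population for the main analysis, and the mITT and PP populations for the repeats. Use the same patient-level count for the 5% threshold that selects the method. Tabulate component events and repeat events separately by arm.

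The cost is a short change to the SAP text, with no new data. The downside is that repeat events no longer enter the Method 2 test; they remain visible in the tables.

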## 6.4 – Expected drop-out rate

We expect a maximum drop-out rate of 22% (i.e. a maximum of 82 patients among the 374 patients are expected to fail to complete the 12-month follow-up).

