4.1.1 The Safety Population

The Safety population will include all randomized Subjects who underwent their first ablation procedure.

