4.3 SECONDARY ENDPOINTS

The secondary endpoints are as follow:

- 1. Freedom from AF/AT after one or two procedures at 12 months following index procedure.
- 2. Freedom from AF/AT after a single procedure at 12 months following index procedure.
- 3. The safety endpoint is a composite endpoint, the events of which it is comprised include that of death, cerebrovascular event, or serious treatment-related adverse event at the 12-month timepoint since initial index procedure (this endpoint is inclusive of the Blanking Period marked by the 3 months immediately following the initial index procedure undergone by each enrolled subject).

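### Safety Method 2 divides by all ablated patients with no allowance for shortened follow-up, so a true excess risk in the Tailored arm is modestly understated

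*SAP*

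**What the plan says.** SAP 4.3 (item 3) sets the safety endpoint as a composite of death, cerebrovascular event or "serious treatment-related adverse event at the 12-month timepoint since initial index procedure". On the analysis set, SAP 4.5 states: "The safety endpoint analysis, regardless of the method employed, will be conducted in the Safety population". SAP 4.1.1 defines that set with no follow-up requirement: "The Safety population will include all randomized Subjects who underwent their first ablation procedure".

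SAP 4.5 then gives two methods.

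- **Method 1** is a Poisson rate model in which "an offset for the log of the number of weeks each subject remained enrolled in the study will be added".
- **Method 2**, for rare events, uses "the proportion defined by the number of composite AEs out of total subjects in the Tailored (treatment) arm" and "the proportion defined by the number of composite AEs out of total subjects in the Anatomical (control) arm". It tests the difference against a margin of 0.025 with the upper limit of a 90% interval. It has no censoring, person-time or unknown-status rule.

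The same analysis is repeated in the mITT and PP sets. The censoring rule in SAP 6.3 covers the main efficacy criterion, and the supportive missing-data analyses promised there cover the primary endpoint. On losses, Protocol 6.4 says that "a maximum of 82 patients among the 374 patients are expected to fail to complete the 12-month follow-up".

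**The concern.** A 12-month risk estimated as events over all ablated patients is correct only if everyone is observed for 12 months or has the event first. A patient who leaves in month 2 without an event stays in the denominator for ten months in which no event can be recorded. Method 2 therefore estimates the risk of an event seen before loss, which is lower than the 12-month risk.

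For a non-inferiority test on an absolute difference, the case that matters is Tailored being worse by the margin. There, equal proportional loss scales down both risks and so scales down their difference. The SAP's expectation that losses will be similar between arms gives no protection.

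This case is not far-fetched. Protocol 7.3 expects longer RF times, a larger ablated area and slightly longer procedures in the Tailored arm. Events after the index procedure are also foreseeable. Deaths and cerebrovascular events count all year, SAP 6.9 anticipates second ablations in 22% to 33% of patients, and Protocol 5.3.7 places redo procedures between months 3 and 9.

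**Working it through.** **Inputs from the documents.** 374 patients, 187 per arm, 22% drop-out (Protocol 6.2 and 6.4; SAP 4.2.2); margin 0.025 and upper 90% limit (SAP 4.5). The plan's drop-out figures reproduce: 0.22 × 374 = 82.28, so 82 patients; 292 / 0.78 = 374.4, so 374. No sample size, power, expected event rate or event timing is given for the safety endpoint.

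**Assumptions.** 187 per arm; true 12-month risks of 4.5% Tailored and 2.0% Anatomical, so the true excess equals the margin; losses spread evenly over the year. The 22% is an upper bound for loss after ablation, because it includes patients never ablated, who are outside the Safety population.

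**Formula.** Expected crude risk = true risk × (1 − loss × late share × 0.5). The late share is the fraction of events spread evenly over the 12 months rather than occurring at the procedure. The 0.5 is the average part of the year left after an evenly spread loss.

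| Loss, Tailored / Anatomical | Late share | Crude risks (%) | Excess (points) | Margin lost | False non-inferiority, score-type interval |
|---|---|---|---|---|---|
| none | any | 4.5 − 2.0 | 2.50 | 0% | 4.3–4.5% |
| 22% / 22% | all | 4.5×0.89 − 2.0×0.89 = 4.005 − 1.780 | 2.225 | 11% | 5.9–6.3% |
| 11% / 11% | all | 4.5×0.945 − 2.0×0.945 = 4.2525 − 1.890 | 2.3625 | 5.5% | 4.7–5.1% |
| 22% / 22% | half | same factor, 0.945 | 2.3625 | 5.5% | about 5% |
| 22% / 22% | none | 4.5 − 2.0 | 2.50 | 0% | 4.4% |
| 22% / 11% | all | 4.005 − 1.890 | 2.115 | 15% | 6.7% |
| 11% / 22% | all | 4.2525 − 1.780 | 2.4725 | 1% | 4.4–4.8% |

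The last column comes from enumeration of the binomial tables and from simulation; ranges show the spread between calculations. If all losses fall between week 1 and month 3, the simulated excess is 2.0 points and false non-inferiority is 7.2%.

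**Dependence on the interval.** SAP 4.5 asks for an exact interval with continuity correction but does not name one.

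- Exact unconditional test, 187 per arm, 5.0% against 2.5%: 3.6% with full follow-up, 4.1% with 10% loss, 4.8% with 22% loss in both arms, 5.6% with 22% Tailored and 10% Anatomical loss, and 3.5% with the reverse.
- Continuity-corrected score test, 4.5% against 2.0%: 2.1% with full follow-up, 2.9% with 22% spread loss, 3.7% with early loss, 3.3% with 22% against 11%.

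**Direction away from the margin** (187 per arm, score test, 22% loss in both arms, constant risk).

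- Equal true risks of 3%: the expected difference stays at 0, and the chance of declaring non-inferiority moves from 36.4% to 38.7%.
- Tailored better, 2% against 4%: the expected difference moves from −2.00 to −1.78 points, and the chance falls from 79.0% to 78.8%.

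**Effect of the remedy.** In simulation, a Kaplan-Meier 12-month risk difference returns about 2.5 points and 4.5% to 4.9% false non-inferiority.

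**The case against.** The strongest reply is that the effect is small, conditional, and not shown to breach the planned error rate. Much of this stands.

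- A reader might infer that every patient lost before month 12 is scored as event-free. That is not so. An event recorded before loss is counted, and death, although Protocol 6.1 and 6.7 list it among losses, is itself a component of the composite. Only patients lost without a recorded event are affected.
- A reader might infer that non-inferiority becomes easier in general. It does so to any material degree only when Tailored is truly worse and losses are similar or heavier in Tailored. With heavier Anatomical loss the effect vanishes.
- A reader might infer a false-positive rate above 5%. The exact test with similar losses, and the continuity-corrected test in every case tried, stay below that. The exact test passed 5% only with markedly heavier Tailored loss.
- A reader might take "No imputation for missing data is planned" as the rule for Method 2. It stands in SAP 4.5.1, on other adverse events, and does not govern the composite.

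The mITT and PP repeats are a partial check. mITT removes patients lost in the blanking period, which covers the early-loss case, but it keeps those lost from month 3 to month 12. Under Protocol 6.1 it may also drop early deaths as losses. PP selects on attendance and on absence of important deviations. Neither estimates the 12-month risk in all ablated patients.

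**Conclusion.** The point holds as a cheap improvement. As written, Method 2 does not estimate the stated 12-month risk when follow-up is incomplete, although Method 1 allows for incomplete follow-up.

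The size is modest. With constant risk and 22% loss in both arms after ablation, a true excess of 2.5 points appears as about 2.2, and false non-inferiority rises by about 1 to 2 percentage points. It is close to nil with loss of about 11% or less, with events clustered at the procedure, or with heavier Anatomical loss. These figures rest on assumed event rates and on assumed timing of events and losses, none of which the documents give. The documents do not support a claim that the planned exact interval exceeds its nominal error when losses are similar between arms. Method 2 is also a fallback for one secondary endpoint.

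**What to change.** In Method 2 of SAP 4.5:

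1. Define P1 and P2 as Kaplan-Meier estimates of the 12-month risk of a first composite event in the Safety population.
2. Code deaths as events, never as losses. Censor patients without an event at their last safety contact.
3. Apply the existing 2.5-point margin to the confidence interval for that difference, for example a score-type interval using the effective sample size from the Greenwood variance.
4. If either arm has no events, use the exact crude-proportion interval, because the Greenwood variance is then zero. With 187 per arm this has probability 0.98^187 = 2.3% at a 2% risk and 0.99^187 = 15% at a 1% risk.
5. Report the crude exact result alongside, with the number of patients in each arm whose 12-month safety status is known.

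The cost is a few lines of SAP text and code. Event onset dates and end-of-participation forms are already collected (Protocol 14.2 and 5.2.3). The drawbacks are a slightly wider interval that is no longer strictly exact, and the remaining assumption that loss is uninformative. If the sponsor prefers to keep the exact interval as the deciding one, the Kaplan-Meier difference should be a pre-specified sensitivity analysis that must agree before non-inferiority is claimed.
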